### **3.6 Subject Replacement**

Subject replacement will not be conducted.

## **4. TRIAL SCHEDULE**

For this 16-week randomised, parallel-design prospective study, subjects are required to attend 6 visits including an initial screening visit. The duration for each visit is estimated to be approximately 5 hr for the pre- and post-intervention visits and approximately 2 hr for the screening and monthly visits in between. Following the initial screening visit, each visit would be separated by a 4-week interval. The trial schedule is depicted in the schematic attached in Appendix 1.

## **5. STUDY DESIGN**

### **5.1 Summary of Study Design**

For this 16-week randomised, parallel-design prospective study, subjects are required to attend 6 visits in total including an initial screening visit. The duration for each visit is estimated to be approximately 5 hr for the pre- and post-intervention visits and approximately 2 hr for the screening and three visits in between. Following the initial screening visit, each visit would be separated by a 4-week interval.

## **6. METHODS AND ASSESSMENTS**

The following study procedure description will not involve the use of any audio or visual recording devices.

### **6.1 Randomisation and Blinding**

Randomisation will be conducted using SAS 9.4 software which will assign the subjects either to

the intervention or control group. Single blinding (investigator) will be practiced.

## **6.2 Contraception and Pregnancy Testing**

For pre-menopausal female subjects, a pregnancy test kit will be provided during each visit to determine for pregnancy during the study duration.

## **6.3 Study Visits and Procedures**

### **6.3.1 Screening Visits and Procedures**

Pre-screening: Volunteers who responded will be interviewed over the phone by a qualified member of the research team. During the phone interview, the volunteer will be given a brief description of the study design and procedures to be followed. This will also include questions on the eligibility to participate in the research study based on a pre-determined set of criteria. If the volunteer is still interested and eligible, with their verbal approval, arrangements will be made for them come down for the screening visit. If the volunteer does not qualify for the study or declines to participate, these data will be destroyed following the completion of the phone conversation.

Screening: Under the guidance of trained study personnel, the volunteers will first be briefed about the study and given ample time to carefully read through the informed consent form. They will also be provided an opportunity to question any doubts before acknowledging the consent form which will be kept by both the study personnel and participant. Participants who gave their acknowledgement will be further assessed for their study eligibility based on a pre-determined set of criteria including the completion of a healthy diet checklist. Following which, participants who fulfilled the previous criteria will be instructed to complete a medical history questionnaire. Based on the collected data, approval for participation will be finalised by either of the study investigators, [name], [name] or [name]. If the participant does not qualify for the study or declines to participate, these data will be destroyed after the screening visit unless otherwise agreed.

### **6.3.2 Study Visits and Procedures**

Prior to each visit, subjects will be required to fast from the night before for approximately 10 to 12 hrs.

The following procedures will be conducted by trained research staff on the pre- and post-

intervention visits:

1. Sampling of fasting-state blood (60 mL) through intravenous cannulation from one of the subject's arms in a room at NUH IMU designated and approved for phlebotomy purposes.
2. Anthropometric measurements including height (pre-intervention visit only), weight and waist circumference at Food Science & Technology Programme, NUS.
3. Blood pressure measurement at Food Science & Technology Programme, NUS.
4. Skin carotenoid status analysis using resonance Raman spectroscopy at Food Science & Technology Programme, NUS.
5. Endothelial-dependent brachial artery FMD and carotid IMT using high-frequency ultrasonographic imaging at the National University Heart Centre
6. Body composition assay by DXA at the Orthopaedic Diagnostic Centre, NUHS
7. Questionnaires and assessment forms including a 3-day food record, Pittsburgh sleep quality index questionnaire, sleep evaluation questionnaire, perceived stress questionnaire, Montreal cognitive assessment, subjective appetite visual analogue scale and quantitative food frequency questionnaire (FFQ: pre-intervention visit only) at Food Science & Technology Programme, NUS.

The following procedures will be conducted by trained research staff on the three visits in between:

1. Sampling of fasting-state blood (20 mL) through intravenous cannulation from one of the subject's arms in a room at NUS OHC designated and approved for phlebotomy purposes.
2. Anthropometric measurements including weight and waist circumference at Food Science & Technology Programme, NUS.
3. Blood pressure measurement at Food Science & Technology Programme, NUS.
4. Skin carotenoid status analysis using resonance Raman Spectroscopy at Food Science & Technology Programme, NUS.
5. Questionnaires and assessment forms including a 3-day food record, Pittsburgh sleep quality index questionnaire and subjective appetite visual analogue scale at Food Science & Technology Programme, NUS.

The collected blood samples will be stored and analysed for the following parameters :

1. Blood lipid-lipoprotein concentrations: Total cholesterol, high-density lipoprotein

cholesterol, low-density lipoprotein cholesterol, and total triglyceride (every 4 weeks).

2. Blood carotenoid concentration: Fasting state lutein, zeaxanthin, lycopene,  $\alpha$ -carotene,  $\beta$ -carotene,  $\alpha$ -cryptoxanthin, and  $\beta$ -cryptoxanthin concentrations using high-performance liquid chromatography (HPLC; pre- and post-intervention only).
3. Oxidative stress and inflammatory-related parameters: Concentrations of plasma oxidative stress (malondialdehyde (MDA), glutathione peroxidase (GPX), and superoxide dismutase (SOD)) and inflammatory (tumour necrosis factor- $\alpha$ , interleukin-6, monocyte chemoattractant protein-1) biomarkers using commercially available ELISA assay kits (pre- and post-intervention only).
4. Concentrations of vasodilation and vasoconstriction-related biomarkers: nitric oxide, endothelial nitric oxide synthase, and endothelin-1 using commercially available ELISA assay kits (pre- and post-intervention only).
5. Endothelial progenitor cells will be analyzed and enumerated using flow cytometry.
6. Lipidomic profiles: The main classes of glycerophospholipids (phosphatidylcholine, phosphatidylserine, phosphatidylglycerol, phosphatidylinositol, phosphatidylserine, including lysoglycerophospholipids) and sphingolipids (sphingomyelin and ceramides) will be analysed at pre- and post-intervention by high-performance liquid chromatography couple with targeted MRM analysis on triple-quadrupole mass spectrometers (pre- and post-intervention only).
7. Additional plasma will be stored for possible further analyses.

At the end of the subject's first visit, they will also be randomised into either the intervention or control arm using SAS 9.4 software although the intervention will only begin the following week.

One-to-one dietary counselling for each subject and an instruction sheet "My Healthy Plate dietary guide" will be provided by a research dietitian and trained research staff to achieve the healthy eating pattern diet while only subjects in the wolfberry intervention group will receive a provision of 500 g dried wolfberries every 4 weeks along with specific instructions to cook and consume 15 g/day wolfberry as part of a mixed-meal. Compliance with the diet interventions will be promoted by frequent online and in-person contact, 3-day food records (every 4 weeks) as well as photographs of the subject's meals which will be sent to the study personnel for regular checks on pre-determined dates.

### **6.3.3 Post Study Follow-up and Procedures**

A monetary stipend of \$ 600 will be issued after the subject's completion of the intervention. However, the monetary stipend will be pro-rated as shown in the table below depending on the number of visits completed if a subject decides to withdraw during the course of study. Volunteers who are deemed ineligible after screening will also be reimbursed \$ 10 for their participation in the screening procedure. Specifics of the amount of reimbursement provided after each visited are described in the following table.

Visit	Financial payment/ incentive
Screening	\$ 10
Visit 1	\$ 150
Visits 2 to 4	\$ 50 each
Visit 5	\$ 300
Total	\$ 610

### **6.3.4 Discontinuation Visit and Procedures**

Subjects who voluntary withdraw during the 16-week intervention will not be replaced and the monetary stipend will be pro-rated according to the point in which they decided to withdraw during the study. No follow-up evaluations are required for subjects who withdraw from the study. However, if withdrawal is attributed to an illness or injury afflicted due to the subject's involvement in the study, NUS will be responsible for all compensations.

## **7. TRIAL MATERIALS**

Dried whole wolfberry (500 g) would be issued to the subjects in the intervention group free of charge every 4 weeks and will be replenished during each visit. Subjects will be advised to consume these wolfberries as a part of a whole meal i.e. by cooking it with rice (wholegrain), a dietary staple in Singapore.

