### **2.2 Hypothesis**

1. Consuming wolfberry with a healthy eating pattern diet will improve endothelial function when compared to a same diet without wolfberry.

2. Consuming wolfberry with a healthy eating pattern diet will improve the whole body carotenoid and oxidative stress status of subjects compared to those who consumed a similar diet without wolfberry.
3. Consuming wolfberry with a healthy eating pattern diet will improve blood and skin carotenoids status while decrease whole body oxidative stress status when compared to a same diet with no wolfberry.

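### Wholegrain-rice advice is written only for the wolfberry arm, so wholegrain intake may differ between arms and any effect of that would be credited to wolfberry

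*Combined protocol and SAP*

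**What the plan says.** Hypothesis 1 in section 2.2 states that wolfberry with the healthy diet "will improve endothelial function when compared to a same diet without wolfberry". Section 11.1 describes the primary contrast, on endothelial function, in the same terms.

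Section 6.3.2 sets out what the arms share and where they part. Shared: "One-to-one dietary counselling for each subject and an instruction sheet", the sheet being the My Healthy Plate guide. Different: the counselling serves "to achieve the healthy eating pattern diet while only subjects in the wolfberry intervention group will receive a provision of 500 g dried wolfberries". That supply is renewed at 4-week intervals, and its recipients also get "specific instructions to cook and consume 15 g/day wolfberry as part of a mixed-meal".

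Section 7 says the berries "would be issued to the subjects in the intervention group free of charge every 4 weeks", and that recipients will be advised to eat them within a meal, "by cooking it with rice (wholegrain), a dietary staple in Singapore".

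Section 11.2 plans a repeated-measures ANOVA with meal, time and their interaction. It names no dietary covariate and no comparison of dietary intake between arms.

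**The concern.** The trial isolates wolfberry only if everything else in the diet is the same by design. Advice on which staple to cook the berries with is a dietary instruction in its own right. If one arm is pointed to wholegrain rice each time it prepares the product, and the other is not, the arms could come to differ in wholegrain intake as well as in wolfberry.

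Such a difference would arise after allocation, so randomisation would not balance it. The outcomes that could be exposed are those that respond to the general diet: lipids, weight, waist, blood pressure and appetite, all measured at every study visit, and the endothelial measures that form the primary outcome. Plasma zeaxanthin is the least exposed, because section 1.1 identifies the berry itself as a source of it. Exclusion criterion 5 removes people who already follow a healthy eating pattern consistently, so entrants have room to change their staple.

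**Working it through.** The plan gives no figure on this point to reproduce. The check is a comparison of the sections, followed by a note on what can and cannot be calculated.

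**Step 1: dietary instructions by arm.**

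| Element | Wolfberry arm | Control arm | Source |
|---|---|---|---|
| One-to-one counselling and My Healthy Plate guide | Yes | Yes | 6.3.2 |
| Wolfberry supplied, 15 g/day | Yes | No | 6.3.2, 7 |
| Instruction to cook and eat within a mixed meal | Yes | None in the available text | 6.3.2 |
| Advice naming wholegrain rice | Yes | None in the available text | 7 |
| Rice supplied, or an amount or frequency of rice set | No | No | 6.3.2, 7 |
| Staple advice within the shared guide | Cannot be read | Cannot be read | Appendix 12, listed only |

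The second row is the intended contrast. The third and fourth rows are not part of it.

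**Step 2: the two descriptions of the wolfberry instruction.** Section 6.3.2 is specific and daily but names only a mixed meal. Section 7 names wholegrain rice but as advice, without amount or frequency. Section 7 introduces the rice with an i.e., which reads as a definition of how the berries are to be taken and not as one example among several. The two sections do not say the same thing.

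**Step 3: would a difference be prevented or seen?** It is not prevented, because no matched instruction for controls is described. It would not be seen in the planned analysis, because the model in section 11.2 contains only arm (meal), time and interaction. The data to see it do exist. A 3-day food record is listed at the pre-intervention visit, the three visits in between and the post-intervention visit, which is 5 records per completer. One is at baseline and 4 are later, so 4 × 3 = 12 recorded days after baseline. Sections 6.3.2 and 10.1 use these records to promote compliance, and no between-arm tabulation is planned.

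**Step 4: size.** The bias in an outcome would be the between-arm difference in wholegrain intake multiplied by the effect of wholegrain on that outcome per unit of intake. The documents give neither factor, so the product cannot be computed.

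**The case against.** The strongest reply is that the background diet is shared by design. Every subject gets the same counselling and guide, and failing to follow the prescribed diet is a withdrawal criterion in section 3.5 with no restriction by arm. If the guide already directs everyone to wholegrain staples, the rice in section 7 is simply the shared diet with berries added, which is the contrast the hypothesis asks for. Moreover, rice is a staple that controls will eat too, so at most the type of rice might differ.

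Much of this stands. A reader might infer that the wolfberry arm receives a daily, reinforced, additional wholegrain meal and that a wholegrain co-intervention is therefore established. The documents do not support that. It joins the daily instruction of section 6.3.2, which names no rice, to the advice of section 7, which sets no frequency. Nothing says that a meal is added, and no rice is supplied. The documented reinforcement (contact, food records, meal photographs) covers the diet interventions generally. Nor can it be said that controls get no matching advice, only that none appears in the available text.

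A reader might also want to attach a false-positive rate. With 20 per arm, a two-sided 5% t-test (38 degrees of freedom), no true wolfberry effect and a bias of b standard deviations, the non-centrality is b × √(20/2). For b = 0.1, 0.2 and 0.3 this is 0.316, 0.632 and 0.949, and the rejection rate is 6.1%, 9.5% and 15.2%. These figures are purely illustrative. The values of b are assumed and linked to no intake in this trial, the same rates would apply to any bias in any trial of this size, and the planned model is a repeated-measures ANOVA. They carry no weight here.

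What the reply does not remove is that the advice naming wholegrain rice is written for one arm, that the two sections describing it disagree, and that no planned analysis would show whether intake diverged. Even if the guide mentions wholegrains, general advice to everyone is not the same as advice attached to a food that one arm is supplied with and asked to cook.

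**Conclusion.** The point holds as a possible and unmonitored difference between the arms. In the available text, explicit wholegrain-rice advice goes to the wolfberry arm only, so wholegrain intake may differ after randomisation, and the planned analysis would credit any effect of that to wolfberry.

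The size is unknown and cannot be derived from the documents; it could be nil. The conclusion assumes that the unseen guide does not already give both arms equivalent staple advice with equal force, and that wholegrain intake can influence at least some of the outcomes. If the guide does give such advice, what remains is the mismatch between sections 6.3.2 and 7 and the absence of a check on intake. The change is worth making because it is cheap now, whereas an unexamined difference would be hard to separate from wolfberry afterwards.

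**What to change.** 1. Reconcile sections 6.3.2 and 7 so that both describe the wolfberry instruction in the same words.
2. Give both arms the same staple advice (rice, wholegrain, as part of a mixed meal), with wolfberry as the only difference, and say so in both sections. If the My Healthy Plate guide already contains this advice, state that and cite Appendix 12.
3. In section 11.2, pre-specify a descriptive table of wholegrain servings by arm and visit, from baseline to the post-intervention visit, using the 3-day food records already collected every 4 weeks.

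Cost: a small added counselling and compliance burden for controls, and a little more work to code the food records and produce the table. No new visit, assay or data collection is needed.

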### **7.1 Trial Product**

The fruit of *Lycium barbarum*, also called wolfberry or goji berry, is a well-known traditional Chinese medicine plant and it has recently become increasingly popular in many countries around the world due to its health promoting properties (26, 27).

## **7.2 Storage and Drug Accountability**

Dried wolfberries will be stored at 4 °C in a conventional refrigerator at all times to maintain product freshness and consistency.

## **8. TREATMENT**

### **8.1 Rationale for Selection of Dose**

Based on studies by Zanchet et al. 2017(14 g/day) and Cheng et al. 2005 (15 g/day) which likewise conducted human clinical interventions with dried wolfberry, favourable outcomes on the cardiovascular health of the subjects post-intervention were observed. Thus, a similar dose of 15 g wolfberry/day would be used.

### **8.2 Specific Restrictions / Requirements and Concomitant therapy**

Dietary supplements which may impact the outcome of interests (e.g. vitamin supplements, antioxidant supplement, fish oil supplements etc.) should not be consumed by the subjects. In addition, if subjects have been prescribed and are taking antihypertensive, cholesterol-lowering or type-2 diabetic medication within the last 5 years prior to the intervention, they would be excluded from the study as well.

Records of all medications (prescription and over the counter), vitamin and mineral supplements, taken by the participant will be obtained from the medical history questionnaire. Eligibility for the study participation will be finalised by either of the study investigators, [name], [name] or [name].

### **8.3 Blinding**

Study personnel, investigators and outcome assessors will be blinded from the subject's assignment. Unblinding of the study personnel will only be done upon completion of the intervention and analytical procedures.

## **9. SAFETY MEASUREMENTS**

The study poses no more than minimal risk to research participants and the research group members will consistently pay attention to assure the participant's safety.

### **9.1 Definitions**

Definitions of UPIRTSO and serious adverse events as well as other safety management procedures will be further elaborated in Sections 9.2 – 9.4.

### **9.2 Collecting, Recording and Reporting of UPIRTSO events to the NHG Domain Specific Review Boards (DSRB) and Serious Adverse Events (SAEs) to the Health Science Authority (HSA)**

Safety analysis for adverse events will be performed after weekly by the study investigators and personnel involved. All problems involving local deaths related to the study or not, will be reported within 24 hours after first knowledge to the NHG DSRB. Any other SAEs will be reported not later than 7 calendar days after first knowledge to the NHG DSRB. Follow-up information will be actively sought and submitted as it becomes available. A complete follow-up report will be submitted within 8 additional days.

Medical and scientific judgements regarding the relatedness and severity of the occurrence will be performed by Principal Investigator [name].

### **9.3 Safety Monitoring Plan**

1) All data will be used solely for research purposes. The blood will be collected by an invasive procedure (intravenous cannulation) following a standard procedure provided by WHO (36) and collected blood samples will be used to measure selected clinical markers of health only. Other research materials will include: medical, diet logs, body composition, FMD and CIMT measurements. The original paper copies of all identifiable data will be kept in locked storage cabinets and rooms with access limited to [name], [name], [name] and her research staff. Electronic copies of the data with identifiable participant information will be kept on a secure website or password-protected computer with access limited to [name], [name], [name] and her research staff. All data will be de-identified prior to statistical analyses

2) Blood Collections: Participants may experience soreness and bruising at the puncture site. Participants may also feel lightheaded and there is a slight risk of fainting. Direct pressure will be applied over the puncture site to minimize soreness and bruising. Participants will be seated in a cushioned chair with padded armrests to minimize the risk of falling if a participant becomes lightheaded or faints during the blood draw. [name] trained research staff will stay with participants at NUHS IMU and NUS OHC during the blood collection to assure the participant's safety. Participants will be asked not to donate blood for at least one month prior to, during, and for one month after the study due to potential alterations in the participant's blood profile that may affect study outcomes. In the unlikely event that the subject is injured while giving a blood sample, first aid will be provided and the subject will be directed to proper health treatment by the on-site study physicians.

3) Dietary Intervention: There is no known risk associated with the consumption of wolfberry or a healthy eating pattern diet according to earlier intervention studies of a similar nature (30–32) but there is a possibility of the stomach or bowels becoming upset if there is a change in usual customary dietary intakes. Subjects who experience these symptoms will be closely monitored and instructed to modify their wolfberry intake pattern by distributing the intake of wolfberry over 3 meals instead. If the symptoms persist, the Principal Investigator and/or the Co-investigator of this study may stop the subject's participation at any time if it is decided that it is in his/her best interests. If significant new findings develop during the course of this research that may relate to the subject's willingness to continue participation, they will be provided with this information.

4) Resonance Raman Spectroscopy: There is no known risk associated with non-invasive resonance Raman spectroscopic analysis which involves only the exposure of the palm to visible blue light.

5) Dual-energy X-ray absorptiometry (DXA): Body composition will be measured through non-invasive procedures. Specifically, body density will be determined using DXA. DXA involves some exposure to radiation; however, it is very small. The average absorbed dose of radiation, per scan, is equal to 1.424 mRem, totaling 4.272 mRem for all 3 scans. This amount of radiation exposure is less than or equal to one percent of the average exposure from a chest x-ray (5-20 mRem), and less than or equal to one-tenth of one percent of the average exposure from a full dental x-ray series (50-300 mRem)

6) High frequency ultrasonographic imaging: Ultrasonographic imaging has been used for over 20 years with excellent record. It is based on non-ionizing radiation and is generally considered safe when used prudently by appropriately trained healthcare providers (37).

